## Appendix A Schedule of procedures for Part A

Visit Number	01	02	03	04	05	06	07	08	09	10	11	12	AESI 
Study Week		0	2	8	10	16	18	32	34	52	54	80	104
Study Month		0	0.5	2	2.5	4	4.5	8	8.5	12	12.5	18	24
Study Day	-56 to 0	0	14	56	70	112	126	224	238	364	378	560	728
Procedure	Screen 	Vac 1		Vac 2		Vac 3		Vac 4		Vac 5			
Study procedures													
Assessment of Understanding	√												
Informed consent	√												
Medical history 	√												
Physical exam 	√	√	√	√	√	√	√	√	√	√	√	√	
Contraception status assessment 	√	√		√		√		√		√			
Risk reduction counseling 	√	√	√	√	√	√	√	√	√	√	√	√	
Concomitant medications 	√	√	√	√	√	√	√	√	√	√	√	√	
Adverse Events (AEs)		√	√	√	√	√	√	√	√	√	√		
AESIs/MAAEs/SAEs		√	√	√	√	√	√	√	√	√	√	√	√
Vaccination 		√		√		√		√		√			
Reactogenicity assessment 		√		√		√		√		√			
Clinical labs	Tube												
Pregnancy test (urine or serum) 	√	√		√		√	√	√	√	√		√	
HBsAg/anti-HCV 	SST	5											
HIV screening test 	SST	5											
CBC/Differential 	EDTA	5	5		5		5		5		5		
ALT & Creatinine 	SST	5	5		5		5		5		5		
HIV diagnostic test	EDTA					10		10		10		20	
Research samples													
PBMC for assays & storage	ACD		136		136		136				178.5	178.5	
Serum for assays and storage	SST		34	34	34		34		34		34	34	
Leukapheresis			√ 						√				
Fine Needle Aspiration 							√						
Daily volume (mL)	20	34	180	0	180	10	180	10	44	10	222.5	232.5	
56-day total volume (mL)	20	54	234	234	360	190	370	10	54	10	232.5	232.5	

**Green shading = Vaccination Visit; Blue shading = FNA visit**

-  **Screening** evaluations at Visit 01 are performed no more than 56 days before Day 0.
-  **Medical history:** A complete medical history is performed during screening. At enrollment and at subsequent visits, an interim medical history may be performed.
-  A complete **physical exam** is performed at screening and last clinic visit, to include height, weight, vital signs, and clinical assessments of head, ears, eyes, nose, and throat; neck, lymph nodes; heart; chest; abdomen; extremities; neurological function; and skin. At other visits, a **targeted physical exam** will be performed as needed, based on participant report or indications of illness.
-  **Contraception status assessment** is required only for participants who were assigned female sex at birth and are capable of becoming pregnant.
-  **Risk reduction counseling** per CRS Standard Operating Procedures.
-  **Concomitant medications**, including prescription and non-prescription drugs, vitamins, topical products, alternative/complementary medicines, recreational drugs, vaccinations, and allergy shots are recorded during screening, at enrolment, and at each subsequent clinic visit.
-  **Vaccination (in clinic assessments):** At least 60 minutes after each vaccination and prior to clinic discharge, participants will have vital signs taken, the injection site will be assessed, and systemic symptoms will be assessed.
-  **Reactogenicity:** Clinic staff will follow new or unresolved reactogenicity symptoms present at day 7 until resolution.
-  **Pregnancy test:** For participants assigned female sex at birth. Pregnancy test may be performed on blood specimens. Persons who are NOT capable of becoming pregnant due to total hysterectomy or bilateral oophorectomy (verified by medical records), or menopause (no menses for  $\geq 1$  year) are not required to undergo pregnancy testing. Persons who are confirmed pregnant, pregnancy testing is not required, unless clinically indicated.
-  Local labs may assign appropriate alternative tube types for locally performed tests.
-  **HIV screening test:** see Section [5.1.1](#).
-  **Research samples:** Blood draw volumes for each tube type shown.
-  **Leukapheresis:** May be performed prior to enrollment visit once the participant has been found to have met all protocol enrollment criteria (see Section [5.1.1](#) and [5.1.2](#)) and leukapheresis eligibility criteria (see Section [8.5](#)). A pregnancy test (see also footnote 9) must be performed and confirmed negative within 48 hours prior to leukapheresis.
-  **Fine Needle Aspiration:** Target for FNA is three weeks post 3rd vaccination. A pregnancy test (see also footnote 9) must be performed and confirmed negative within 48 hours prior to lymph node cell collection.
-  **AESI contact:** CRS staff will contact study participants 12 months after the last vaccination received to collect the information listed in Section [8.9](#).

## Appendix B Schedule of procedures for Part B

Visit Number		01	02	03	04	05	06	07	08	09	10	11	12	AESI 
Study Week			0	2	8	10	16	18	32	34	52	54	80	104
Study Month			0	0.5	2	2.5	4	4.5	8	8.5	12	12.5	18	24
Study Day		-56 to 0	0	14	56	70	112	126	224	238	364	378	560	728
Procedure		Screen 	Vac 1		Vac 2		Vac 3		Vac 4		Vac 5			
Study procedures														
Assessment of Understanding		√												
Informed consent		√												
Medical history 		√												
Physical exam 		√	√	√	√	√	√	√	√	√	√	√	√	
Contraception status assessment 		√	√		√		√		√		√			
Risk reduction counseling 		√	√	√	√	√	√	√	√	√	√	√	√	
Concomitant medications 		√	√	√	√	√	√	√	√	√	√	√	√	
Adverse Events (AEs)			√	√	√	√	√	√	√	√	√	√		
AESIs/MAAEs/SAEs			√	√	√	√	√	√	√	√	√	√	√	√
Vaccination 			√		√		√		√		√			
Reactogenicity assessment 			√		√		√		√		√			
Clinical labs	Tube													
Pregnancy test (urine or serum) 		√	√		√		√		√		√		√	
HBsAg/anti-HCV 	SST	5												
HIV screening test 	SST	5												
CBC/Differential 	EDTA	5		5		5		5		5		5		
ALT & Creatinine 	SST	5		5		5		5		5		5		
HIV diagnostic test	EDTA						10		10		10		20	
Research samples														
PBMC for assays & storage	ACD		136	136		136		136		136		178.5	178.5	
Serum for assays and storage	SST		34	34		34		34		34		34	34	
Daily volume (mL)		20	170	180	0	180	10	180	10	180	10	222.5	232.5	
56-day total volume (mL)		20	190	370	370	360	190	370	10	190	10	232.5	232.5	

-  **Screening** evaluations at Visit 01 are performed no more than 56 days before Day 0.
-  **Medical history:** A complete medical history is performed during screening. At enrollment and at subsequent visits, an interim medical history may be performed.
-  A complete **physical exam** is performed at screening and last clinic visit, to include height, weight, vital signs, and clinical assessments of head, ears, eyes, nose, and throat; neck, lymph nodes; heart; chest; abdomen; extremities; neurological function; and skin. At other visits, a **targeted physical exam** will be performed as needed, based on participant report or indications of illness.
-  **Contraception status assessment** is required only for participants who were assigned female sex at birth and are capable of becoming pregnant.
-  **Risk reduction counseling** per CRS Standard Operating Procedures.
-  **Concomitant medications**, including prescription and non-prescription drugs, vitamins, topical products, alternative/complementary medicines, recreational drugs, vaccinations, and allergy shots are recorded during screening, at enrolment, and at each subsequent clinic visit.
-  **Vaccination (in clinic assessments):** At least 60 minutes after each vaccination and prior to clinic discharge, participants will have vital signs taken, the injection site will be assessed, and systemic symptoms will be assessed.
-  **Reactogenicity:** Clinic staff will follow new or unresolved reactogenicity symptoms present at day 7 until resolution.
-  **Pregnancy test:** For participants assigned female sex at birth. Pregnancy test may be performed on blood specimens. Persons who are NOT capable of becoming pregnant due to total hysterectomy or bilateral oophorectomy (verified by medical records), or menopause (no menses for  $\geq 1$  year) are not required to undergo pregnancy testing. Persons who are confirmed pregnant, pregnancy testing is not required, unless clinically indicated.
-  Local labs may assign appropriate alternative tube types for locally performed tests.
-  **HIV screening test:** see Section [5.1.1](#).
-  **Research samples:** Blood draw volumes for each tube type shown.
-  **AESI contact:** CRS staff will contact study participants 12 months after the last vaccination received to collect the information listed in Section [8.9](#).

## Appendix C Visit windows for Part A and Part B

Visit Number	Visit Type	Lower Allowable Window (-)	Lower Target Window (-)	Target Day*	Upper Target Window (+)	Upper Allowable Window (+)
01.0	Screening	-56	-	0	-	+0
02.0	Enrollment/Vaccination 1	-	-	0	-	-
03.0	2 weeks post-vaccination 1		-4	14	+4	+7
04.0	Vaccination 2		-7	56	+9	+14
05.0	2 weeks post-vaccination 2		-4	70	+4	+7
06.0	Vaccination 3	-21	-14	112	+14	+21
07.0**	2 weeks post-vaccination 3 Primary Immunogenicity	-	-4	126	+4	+21
08.0	Vaccination 4	-28	-14	224	+14	+28
09.0	2 weeks post-vaccination 4	-	-4	238	+4	+7
10.0	Vaccination 5		-28	364	+28	
11.0	2 weeks post-vaccination 5		-4	378	+4	+7
12.0	Final Visit	-28	-14	560	+14	+28
AESI	AESI Contact	-28	-14	728	+14	+28

\* All target dates are relative to Day 0, with the exception of the post-vaccination visits, visits 3.0, 5.0, 7.0, 9.0, and 11.0 which are relative to the vaccination immediately preceding the visit.

\*\* Target date for FNA is three weeks post 3rd vaccination, see HVTN 300 Study Specific Procedures (SSP) for more details.

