### **3 Objectives and endpoints for Part A and Part B**

#### **3.1 Primary objectives and endpoints**

*Primary objective 1:*

To evaluate the ability of the vaccine regimen to elicit CD4 binding-site, V2 apex and V3 glycan (bnAb region at the base of the V3 loop), and CH505TF-specific memory B cells

*Primary endpoint 1:*

Flow cytometry analysis of the frequency of the CD4 binding-site, V2 apex and V3 glycan (bnAb region at the base of the V3 loop), and CH505TF-specific IgG+ B cells

*Primary objective 2*

To evaluate the ability of the vaccine regimen to elicit autologous tier 2 virus neutralizing antibodies

*Primary endpoint 2:*

Response rate and magnitude of serum antibody neutralization of vaccine-matched tier 2 HIV-1 strains as measured by TZM-bl assay

*Primary objective 3:*

To evaluate the safety and tolerability of a 300 mg dose of CH505 TF chTrimer admixed with different adjuvant regimens

*Primary endpoint 3:*

Local and systemic reactogenicity signs and symptoms will be collected for a minimum of seven days following receipt of any study vaccine.

Serious adverse events (SAEs), medically attended adverse events (MAAEs), adverse events of special interest (AESIs) and AEs leading to early participant withdrawal or permanent discontinuation which will be collected throughout the study and for twelve months following any receipt of study product. Additionally, all adverse events will be collected for 30 days after any receipt of study vaccination.

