## **5.2 Participant departure from vaccination schedule or withdrawal**

### **5.2.1 Delaying vaccinations for a participant**

Under certain circumstances, a participant's scheduled vaccination will be delayed. The factors to be considered in such a decision include but are not limited to the following:

- Intercurrent illness or pre-vaccination abnormal vital signs or clinical symptoms that may mask assessment of vaccine reaction

- Treatment with systemic glucocorticoids (eg, prednisone or other glucocorticoid), immune targeting monoclonal antibodies or other immunomodulators (other than nonsteroidal anti-inflammatory drugs [NSAIDs]), with the exception that study injection may continue per PI discretion if the next study injection occurs at least 2 weeks following completion of glucocorticoid treatment;
- Receipt of any live attenuated vaccines within 4 weeks prior to study vaccine administration; (Note: ACAM2000 vaccine for Monkeypox received within 30 days prior to enrollment or receipt of study vaccine; or if ACAM2000 received greater than 30 days prior to enrollment or receipt of study vaccine and vaccination scab still present; or planned administration within 30 days after enrollment or receipt of study vaccine).
- Receipt of any vaccines that are not live attenuated vaccines within 2 weeks prior to study vaccine administration. Replication incompetent vaccines such as the Jynneos vaccine for the prevention of monkeypox disease are not considered to be live vaccines.

Vaccinations should not be administered outside the visit window period specified in [Appendix C](#) without PSRT approval.

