## 6 Statistical considerations

### 6.1 Sample size justification and accrual

Recruitment will target enrolling a total of 48 healthy, HIV-uninfected adult participants in 4 groups.

In Part A, recruitment will target enrolling 12 healthy, HIV-uninfected adult participants in Group 1. The protocol team will convene after the 12th participant has received their third vaccination to determine if further participants should be enrolled to evaluate immunogenicity. Examples of reasons that might necessitate enrollment of additional participants are provided in Section 1.5. If some participants from the original number of 12 enrolled will not contribute data to some of the immunogenicity analyses, the protocol team may enroll additional fully evaluable participants, up to 6 additional participants, or a total of 18 participants enrolled, with the goal of at least 12 contributing to the final immunogenicity analyses.

In Part B, recruitment will target enrolling a total of 36 healthy, HIV-uninfected adult participants in Groups 2, 3, and 4 ( $n = 12$  participants per group). Enrollment in Groups 2, 3, and 4 will be stepwise by group, starting with Group 2, continuing with Group 3, and finishing with Group 4.

Every study participant will be followed for an AESI contact 12 months after the last vaccination received (for example, following participants until Month 16 if they receive 3 vaccinations, or Month 24 if they receive 5 vaccinations).

Detail about the pace of enrollment can be found in Section 1.5.

Since enrollment is concurrent with receiving the first vaccination, all participants will provide some safety data. However, for immunogenicity analyses, data may be missing for a variety of reasons, including participants terminating from the study early, problems in shipping specimens, or high assay background. Immunogenicity data from 17 Phase 1 and 2 Phase 2a HVTN vaccine trials, which began enrolling after June 2005 (data as of September 2014), indicate that 17% is a reasonable estimate for the rate of missing data.

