## 8.9 AEFI contact

CRS staff will contact study participants 12 months after the last vaccination to collect the information listed below. If indicated, the participant may be asked to come in for a clinical assessment which may also include referrals for AEFI assessment. AEFIs are described further in [Appendix H](#).

- Confirmation of vital status; if deceased, attempt to learn cause and date of death
- If participant is alive, record the participant's responses to the following:
- SAEs
- AEFI (a sample list of AEFIs is provided in [Appendix H](#)). AEFIs are reported regardless of relationship to study product(s);
- MAAEs, defined as any adverse events leading to an unscheduled visit to a healthcare professional which are reported regardless of relationship to study product(s);
- New diagnosis of HIV infection; and
- Pregnancies and outcomes, including congenital anomalies/birth defects.
- All such events will be recorded and adverse events will be assessed for relationship to study vaccines.

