## 9 Safety and adverse events

### 9.1 Adverse events

Unsolicited AEs will be collected over a period of 30 days after each vaccination. All collected AEs are captured in the clinical database on the appropriate CRF. Clinic staff should evaluate every AE to determine if (1) the AE meets the requirements for expedited reporting (see Section 9.2.1), (2) if the AE meets the criteria for a safety pause/prompt AE review (see Section 9.7), (3) if the AE meets the criteria for an MAAE, and (4) if the AE is a potential immune-mediated disease that may be listed as an AE of special interest (AESI). A sample list of AESIs is provided in [Appendix H](#).

In addition, a limited set of AEs will be collected and reported for 12 months following the any vaccine administration

- SAEs/EAEs,
- AESIs,
- MAAEs (defined as any adverse events leading to an unscheduled visit to a healthcare professional)
- AEs leading to early participant withdrawal or early discontinuation of study vaccine(s) administration.

Adverse events (AEs) will be graded according to the Division of AIDS (DAIDS) Table for Grading the Severity of Adult and Pediatric Adverse Events, Corrected Version 2.1 (<https://rsc.niaid.nih.gov/clinical-research-sites/daids-adverse-event-grading-tables>), with the following exceptions:

- Unintentional Weight Loss is required to be reported as an AE only if it is considered to be potentially deleterious to the participant's health (see HVTN 300 SSP);
- Creatinine is required to be reported as an AE only if it is gradable per the increase from local lab ULN parameter. Do not grade elevated creatinine based on the change from the baseline parameter.
- Do not grade creatinine clearance or eGFR based on the change from the baseline parameter. Do not grade on the basis of eGFR if there is clinical concern for kidney injury.

- Injection Site Erythema or Redness and Injection Site Induration or Swelling will not consider surface area and interference with usual social and functional activities such that:
  - Grade 1 is: 2.5 to < 5 cm in diameter;
  - Grade 2 is:  $\geq 5$  to < 10 cm in diameter;
  - Grade 3 is:  $\geq 10$  cm in diameter OR Ulceration OR Secondary infection OR Phlebitis OR Sterile abscess OR Drainage;
  - Grade 4 is: Potentially life-threatening consequences (eg, abscess, exfoliative dermatitis, necrosis involving dermis or deeper tissue);

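### Appendix C ties the AESI contact to Day 0, but the rest of the protocol ties it to the last vaccination, so an in-window contact can fall up to 56 days short of 12 months

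*Protocol*

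**What the plan says.** **Appendix C (visit windows).** The footnote reads "All target dates are relative to Day 0, with the exception of the post-vaccination visits, visits 3.0, 5.0, 7.0, 9.0, and 11.0". Those five visits are counted from the preceding vaccination. The AESI row reads "AESI Contact -28 -14 728 +14 +28" and is not in the list, so its anchor is Day 0. Vaccination 5 has target Day 364 with a window of 28 days on either side.

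**Places that anchor the contact to the last dose.**
- Section 8.9: "CRS staff will contact study participants 12 months after the last vaccination".
- Section 6.1 gives worked examples: "following participants until Month 16 if they receive 3 vaccinations, or Month 24 if they receive 5 vaccinations".
- Section 1.6, Appendix A footnote 15 and Appendix B footnote 13 say the same in substance, as does SAP Section 3.6.

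**What the endpoint needs.** Under primary endpoint 3 (Section 3.1), SAEs, MAAEs, AESIs and AEs leading to withdrawal or discontinuation are "collected throughout the study and for twelve months following any receipt of study product". Section 9.1 agrees: "a limited set of AEs will be collected and reported for 12 months following the any vaccine administration".

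**Which table sites use.** Sections 8.2 and 8.6 refer to Appendix C for visit windows. On dosing, Section 5.2.1 says "Vaccinations should not be administered outside the visit window period specified in" Appendix C unless the PSRT approves.

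**The concern.** The protocol gives two rules for when primary safety follow-up ends. The one in the window table, by which a contact is judged on time, takes no account of when the last dose was given. A contact can therefore be in window and still come before the 12 months that the endpoint requires.

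This contact carries much of the endpoint. The last scheduled clinic visit is Day 560, which is 560 − 364 = 196 days after an on-time fifth dose. After that, SAE, MAAE and AESI collection rests on the single AESI contact. The AESIs in Appendix H are mainly potential immune-mediated diseases, for which the later months matter.

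The SAP would not show a shortfall. It repeats the endpoint (Section 4), analyses all data (Section 10) and lists AESIs and MAAEs (Section 11). It does not ask for the time from last dose to last safety contact, so follow-up could differ between participants without being visible.

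**Working it through.** **Inputs.** From Appendix C: Vaccination 5 on Day 364 ± 28, so Days 336 to 392; AESI contact on Day 728, target window ± 14 (Days 714 to 742), allowable window ± 28 (Days 700 to 756). Conversion used here: 1 month = 365.25/12 = 30.44 days.

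**Step 1. The protocol's own figure.** Target to target, 728 − 364 = 364 days, or 364/30.44 = 11.96 months. This reproduces the stated 12 months. The schema and schedules also equate Month 12 with Day 364 and Month 24 with Day 728, so 12 months means 364 days in this protocol.

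**Step 2. Five doses, Appendix C used alone.** Interval = contact day − day of Vaccination 5.

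| Vaccination 5 | Contact | Days | Months | Short of 364 |
|---|---|---|---|---|
| Day 364 (target) | Day 700 (earliest allowable) | 336 | 11.0 | 28 |
| Day 392 (latest) | Day 728 (target) | 336 | 11.0 | 28 |
| Day 392 | Day 714 (earliest in target window) | 322 | 10.6 | 42 |
| Day 392 | Day 700 (earliest allowable) | 308 | 10.1 | 56 |
| Day 392 | Day 756 (latest allowable) | 364 | 12.0 | 0 |
| Day 336 (earliest) | Day 756 | 420 | 13.8 | none |

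**Step 3. Where the 56 days come from.** If the contact were anchored to the last dose and kept its −28-day allowance, the minimum would be 364 − 28 = 336 days. Re-anchoring therefore recovers 336 − 308 = 28 days. The other 28 come from the early side of the window.

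**Step 4. Can both rules be met with five doses?** Vaccination 5 on Days 336 to 392 plus 364 days gives Days 700 to 756, exactly the allowable AESI window. So every in-window fifth dose has an in-window contact day at 12 months.

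**Step 5. Early stoppers, last dose on its target day.**

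| Last dose | Last dose + 364 | Interval under Appendix C (Days 700 to 756) |
|---|---|---|
| Vaccination 3, Day 112 | Day 476 (15.6 months, the protocol's Month 16) | 588 to 644 days (19.3 to 21.2 months) |
| Vaccination 4, Day 224 | Day 588 | 476 to 532 days (15.6 to 17.5 months) |

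Widening the windows does not help. The latest allowable Vaccination 3 is Day 112 + 21 = 133, and 133 + 364 + 28 = Day 525. The latest allowable Vaccination 4 is Day 224 + 28 = 252, and 252 + 364 + 28 = Day 644. Both fall before Day 700.

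**The case against.** The strongest reply is that the intent is clear. Five places in the protocol, and the SAP, anchor the contact to the last dose. Two of them are footnotes attached to the AESI column of the schedules that sites work from. Only one general footnote in Appendix C differs. A site that follows Section 8.9 or the schedule footnotes always has an in-window day at 12 months for a five-dose participant (Step 4). The 308-day case needs a fifth dose on its last in-window day, a contact on its first allowable day, and a site guided by Appendix C alone. All of this is right, and it makes the point an inconsistency to be reconciled. It does not remove it. A dose on Day 392 with a contact exactly on target is already 28 days short, and nothing in Appendix C prompts a site to adjust for the dose date.

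Three stronger readings are tempting, and the documents do not support them.

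- A reader might infer that the protocol's rule is follow-up from Day 0, ending at about 10 months. That is one table's literal reading, contradicted elsewhere in the same protocol.
- A reader might infer that after a Day 392 dose no in-window contact reaches 12 months. That needs a 365-day year. By the protocol's own calendar, Day 392 to Day 756 is 364 days, which is 12 months.
- A reader might infer that late events are certainly lost, or that short follow-up is counted as complete. Neither document defines a completeness count. Section 9.2.1 keeps SUSAR-category reporting after study completion for events learned of passively. That is only partial cover, since it would not capture all AESIs or MAAEs.

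**Conclusion.** The concern holds as an internal contradiction with a bounded effect. For five-dose participants, Appendix C used alone allows follow-up from 308 to 420 days after the last dose. The worst shortfall is 56 of 364 days (56/364 = 15%), half of it from the anchor and half from the early window. For those who stop after three or four doses the two rules cannot both be met, and Appendix C makes follow-up longer than 12 months.

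Assumptions: Day 392 is taken as the latest in-window fifth dose, because the allowable-window cells for Vaccination 5 are blank in the text and only its ± 28-day target window is given. A later dose approved by the PSRT would shorten the interval further under a Day 0 anchor. The early-stopper intervals in days assume the last dose on its target day. How often sites would schedule by Appendix C alone cannot be told from the documents.

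**What to change.** 1. **Appendix C.** Add the AESI contact to the footnote's exceptions, relative to the last vaccination received, with a target of 364 days. This is the anchor the protocol already states in five other places.
2. **Early side of the window.** Reconcile it with the 12-month endpoint so that an in-window contact cannot fall before 364 days. Re-anchoring alone would still allow 336.
3. **SAP.** Report, by group, the days from last dose to last safety contact and the number of participants who reach 364 days. The threshold should not be 365: a participant dosed on Day 364 and contacted on Day 728, both exact targets, would then be recorded as incomplete.

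**Cost.** One footnote, one table row and a short summary built from dates already collected. No visit is added. Some five-dose contacts move up to eight weeks later (from Day 700 to Day 756 after a Day 392 dose). Contacts for early stoppers move earlier than Appendix C now implies: from Day 728 to about Day 476 after three doses (252 days, 36 weeks) and to about Day 588 after four (140 days, 20 weeks).
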